11.5 Immune related Response Criteria (irRC)

Proprietary of MD Anderson Cancer Center

New, measurable lesions	Incorporated into tumor burden
New, non- measurable lesions	Do not define progression (but precludes irCR)
Non-index lesions	Contribute to defining irCR (complete disappearance is required)
Complete response (CR)	Disappearance of all lesions in two consecutive observations not less than 4 weeks apart
Partial response (PR)	$\geq 50\%$ decrease in tumor burden compared with baseline in two observations at least 4 weeks apart
Stable disease (SD)	50% decrease in tumor burden compared with baseline cannot be established nor 25% increase compared with nadir
Progression of disease (PD)	$\geq 25\%$ increase in tumor burden compared with nadir (at any single time point) in two consecutive observations at least 4 weeks apart

Note: According to the irRC, disease progression of non-index lesions or appearance of new non-measurable lesions will not classify the subject as PD, and therefore the subject may stay in the study if it is in the subject's best interest. A confirmatory tumor assessment may be performed no less than 4 weeks after the first indication of progression to provide additional data for the investigator to decide if the subject should stay in the trial or be discontinued due to clinical progression based on the investigator's decision.

11.6 Time -to- Event Assessment of Response

Time to Response: From the start of study drug to the first observation of a response (the first of two confirmatory measurements).

Duration of Response: From the first observation of a response (the first of the two confirmatory statements) to the first observation of progressive disease, or to death due to any cause, or early discontinuation of treatment due to progressive disease.

Time to Progression: From the start of study drug to the first evidence of progression.

Progression-free survival (PFS): Time from the start of the study drugs until disease progression (based on RECIST 1.1 criteria) or death

Survival: Survival will be calculated from the start of the study drugs to death due to any cause.

Patients in Long Term Extension Phase will not have formal RECIST measurements. The treating physician will evaluate patient for overall continued benefit.

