3.4 Updated results from the present protocol

From May 2017 through February 2020, 42 patients were enrolled in the present trial. At data cutoff (September 21, 2020), 12/42 patients (28.6%) continued to receive trial treatment. The median follow-up time was 18.7 months (95% CI 13.5 to 24.3). Sitravatinib (MGCD516) starting doses of 60, 80, 120, and 150 mg daily were selected according to the late-onset efficacy-toxicity (LO-EffTox) design for 0, 15 (35.7%), 24 (57.1%), and 3 (7.1%) patients. Overall, regardless of sitravatinib starting dose, the combination of sitravatinib plus nivolumab yielded an objective response rate (ORR) of 35.7% (15/42 patients) and a disease control rate (DCR) of 88.1% (37/42 patients). Complete response was noted in one patient (2.4%), who received a sitravatinib starting dose of 80 mg. The posterior mean for the median progression free survival (PFS) was 11.7 months [95% credible interval (CrI) 8.2 to 16.6]. Median overall survival (OS) was not reached, and 34/42 patients (80.1%) were alive at the time of data cutoff. Because we designed our trial to reflect the patient population enrolled in the CheckMate 025 phase III trial of nivolumab monotherapy in advanced ccRCC, we performed historical comparisons with CheckMate 025 using conservative Bayesian non-informative priors. Combining the three sitravatinib dose groups, the posterior probabilities that sitravatinib plus nivolumab yielded higher ORR and longer PFS than those reported for nivolumab monotherapy in CheckMate 025 were 96% and 100%, respectively.

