11.0 CRITERIA FOR RESPONSE OR PROGRESSION

11.1 Efficacy Assessments

Progression-free survival (PFS) and objective response rate (ORR), each based on RECIST 1.1 criteria, are two of the primary efficacy assessments of this study.

Evaluation of response will follow the Response Evaluation Criteria in Solid Tumors (RECIST). All tumor measurements must be recorded in centimeters.

- Target Lesions:
All measurable lesions up to a maximum of 2 lesions per organ and 5 lesions in total, representative of all involved organs, should be identified as target lesions and recorded and measured at baseline. Target lesions should be selected on the basis of their size (those with the longest diameter) and their suitability for accurate repeated measurements (either by imaging techniques or clinically). A sum of the longest diameter for all target lesions will be calculated and reported as the baseline sum longest diameter. The baseline sum of longest diameters will be used as the reference by which the objective tumor response is characterized.
- Non-target Lesions:
All other lesions (or sites of disease) up to 2 lesions per site and 5 lesions in total should be identified as non-target lesions and should also be recorded at baseline. Measurements of these lesions are not required, but the presence or absence of each should be noted throughout follow-up.

Proprietary of MD Anderson Cancer Center

11.2 Evaluation of Target Lesions:

- Complete Response (CR):
The disappearance of all target lesions.
- Partial Response (PR):
At least a 30% decrease in the sum of the longest diameter of target lesions, taking as reference the baseline sum longest diameter.
- Progressive Disease:
At least a 20% increase in the sum of the longest diameter of target lesions, taking as reference the smallest sum longest diameter recorded since the treatment started or the appearance of one or more new lesions.
- Stable Disease:
Insufficient shrinkage to qualify for partial response, or insufficient increase to qualify for progressive disease, taking as reference the smallest sum longest diameter since the treatment started.

11.3 Evaluation of Non-target Lesions:

- Complete Response:
The disappearance of all non-target lesions.
- Incomplete Response/Stable Disease:
The persistence of one or more non-target lesion(s)
- Progressive Disease:
The appearance of one or more new lesions and/or unequivocal progression of existing non-target lesions.

11.4 Evaluation of Best Overall Response:

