The best overall response is the best response recorded from the start of treatment until disease progression/recurrence (taking as reference for progressive disease the smallest measurements recorded since the treatment started).

Evaluation of Best Overall Response (RECIST)

Target Lesions	Non-target lesions	New lesions	Overall response
CR	CR	No	CR
CR	Incomplete response/SD	No	PR
PR	Non-PD	No	PR
SD	Non-PD	No	SD
PD	Any	Yes or no	PD
Any	PD	Yes or no	PD
Any	Any	Yes	PD

CR= complete response; PR= partial response; SD= stable disease; and PD= progressive disease

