14.0 STATISTICAL CONSIDERATIONS / DATA ANALYSIS

14.1 Phase I-II Dose-Finding Design

This is a phase I-II dose-finding trial to determine the optimal dose of the targeted oral agent MGCD516 when combined with immunotherapy via Nivolumab at fixed dose 240 mg IV every 2 weeks, in patients with metastatic renal cell carcinoma with clear cell component who have had prior treatment with anti-VEGF agents. The scientific goal of the trial is to determine an optimal MGCD516 dose level among the four levels **60, 80, 120, 150** mg/day given orally each day until toxicity of progressive disease. Dose-finding will be done using the sequentially adaptive phase I-II late-onset EffTox (Lo-EffTox) trade-off-based design of Jin et al.⁶⁰⁻⁶² For the goal of determining an optimum dose, dose limiting Toxicity within 12 weeks from the start of therapy is defined as described in section 5.3, and Efficacy is defined as achieving CR, PR, or stable disease within 6 weeks. Patients who have received at least 6 infusions of nivolumab 240 mg IV every 2 weeks with no DLTs related to nivolumab, will have the option to transition to the equivalent nivolumab schedule of 480 mg IV every 4 weeks. Because such a change will occur after at least 12 weeks from study initiation the endpoints are not affected for the purpose of dose escalation and de-escalation.

[figure not shown]
Each cohort will include no more or less than 3 patients. A maximum of 60 patients will be treated in up to 20 cohorts of size 3, with the first cohort treated at **80** mg/day, all successive

Proprietary of MD Anderson Cancer Center

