doses chosen by the Lo-EffTox method, and no untried dose level skipped when escalating. Enrollment will continue without delay except, we also require at least one patient's toxicity outcome to have been observed at the current dose (which takes a maximum of 12 weeks) before enrolling the next cohort of patients. For the two Lo-EffTox dose acceptability rules, the upper limit on the probability of toxicity is .40, the minimum probability of Efficacy .50, and cut-offs .10 will be used for both stopping probability criteria. If the lowest dose level is found to be unacceptable in terms of either high toxicity or low efficacy, the trial will be terminated and no dose level will be selected. The three equivalent trade-off probability pairs used for computing the trade-off contours are (.50, 0), (.70, .25), (1, .65). The prior hyper-parameters were computed based on the assumed prior means $\text{Prob}(\text{Efficacy} | \text{dose}) = .25, .30, .35, .50$ and $\text{Prob}(\text{Toxicity} | \text{dose}) = .20, .25, .30, .40$, respectively, at the four MGCD-516 dose levels. The overall prior effective sample size = 1.

The Lo-EffTox design will be implemented using the specialized computer program developed by Jin et al.⁶⁰ The study biostatistician [name], [name], or [name] in the Biostatistics Department should be consulted as necessary during trial conduct. Secondary outcomes will include progression-free survival (PFS) time, overall survival (OS) time, objective response rate (ORR), and quality of life (QOL). Unadjusted distributions of the time-to-event outcomes will be estimated using the method of Kaplan and Meier⁶⁸ and their relationship to prognostic covariates will be evaluated by Bayesian piecewise exponential survival regression.⁶⁹

A Toxicity/Efficacy Summary will be submitted to IND Office Medical Monitor; every three patients, after the first twelve weeks of study therapy or administration is discontinued, whichever comes first, until 60 patients have completed study therapy.

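### Section 11.4 lets a single recorded CR or PR count as a response while section 11.6 presupposes two, so ORR may include unconfirmed responses

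*Combined protocol and SAP*

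**What the plan says.** - **What ORR is based on.** Section 11.1 uses RECIST 1.1 and gives ORR high standing: PFS and "objective response rate (ORR), each based on RECIST 1.1 criteria, are two of the primary efficacy assessments". Section 14.1 ranks it lower: "Secondary outcomes will include progression-free survival (PFS) time, overall survival (OS) time, objective response rate (ORR), and quality of life (QOL".
- **Best overall response (11.4).** "The best overall response is the best response recorded from the start of treatment until disease progression/recurrence". The table that follows combines target, non-target and new lesions. It mentions neither a repeat assessment nor a minimum interval.
- **Time to response (11.6).** It runs to the "first observation of a response (the first of two confirmatory measurements".
- **Duration of response (11.6).** "From the first observation of a response (the first of the two confirmatory statements". Neither definition gives an interval between the two.
- **irRC (11.5).** This is the only place with an explicit interval. A PR there needs a "decrease in tumor burden compared with baseline in two observations at least 4 weeks apart", and CR is treated in the same way. Section 11.1 does not base ORR on irRC.
- **Scans (10.4).** Week 6, week 12, then every 12 weeks while the patient is on protocol therapy. No separate confirmation scan is scheduled.
- **Results (3.4).** An "objective response rate (ORR) of 35.7% (15/42 patients") is reported. The posterior probability of a higher ORR than with nivolumab alone is given as 96%. Section 3.2.3.2 gives the nivolumab ORR as 25%. Confirmation status is not stated for either figure.

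**The concern.** Sections 11.4 and 11.6 do not describe the same responder. Take a patient with a PR at week 6 that is gone at week 12 without progression. Under 11.4 the best response is PR and the patient enters the ORR numerator. Under 11.6 there is no pair of confirming measurements, so no date from which to count time to response or duration.

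Confirmed responders are a subset of best-ever responders, so a confirmation rule can lower the ORR count or leave it unchanged. Taking the most favourable of several readings also tends to bias a response rate upward, and no concurrent arm is read under the same rule.

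Two statements in section 3.4 rest wholly or partly on ORR: the comparison with the historical 25%, and the preference for 120 mg over 80 mg (9/24 against 4/15 responders).

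**Working it through.** **Inputs.** Responders 15 of 42; by dose, 9 of 24 at 120 mg and 4 of 15 at 80 mg; stated posterior probabilities 96% (against history) and 80.7% (120 against 80 mg), all from section 3.4. Historical ORR 25%, from section 3.2.3.2. Section 3.4 calls its priors for the historical comparison non-informative but does not give their form, so symmetric Beta(a, a) priors with a = 0.01, 0.5 and 1 are assumed. The numbers of unconfirmed responses below are also assumptions.

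**Step 1: reproduce the plan's figures.** 15/42 = 35.7%. With y responders, the posterior is Beta(y + a, 42 − y + a). For y = 15, P(ORR > 0.25) is 0.934 (a = 0.01), 0.942 (a = 0.5) and 0.949 (a = 1). The uniform prior comes within about 1 point of the stated 96%. If the historical rate is also treated as uncertain (25% of an assumed 300 to 500 patients), the results are about 0.92 to 0.94. With the prior and historical denominator unstated, the gap is not evidence of an error.

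**Step 2: remove unconfirmed responses.** Each is worth 1/42 = 2.4 points of ORR.

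| Assumed unconfirmed | Confirmed ORR | P(ORR > fixed 25%), a = 0.01 to 1 |
|---|---|---|
| 0 | 15/42 = 35.7% | 0.934–0.949 |
| 1 | 14/42 = 33.3% | 0.878–0.904 |
| 2 | 13/42 = 31.0% | 0.795–0.834 |
| 3 | 12/42 = 28.6% | 0.683–0.737 |
| 5 | 10/42 = 23.8% | 0.405–0.477 |

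The first loss costs about 4 to 6 points of posterior probability, the second about 7 to 8, the third about 10 to 11.

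**Step 3: 120 mg against 80 mg.** With independent Beta posteriors and the same priors, P(ORR at 120 mg > ORR at 80 mg) is:

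- 9/24 against 4/15: 0.740–0.772
- 8/24 against 4/15 (one 120 mg response unconfirmed): 0.650–0.684
- 7/24 against 4/15 (two unconfirmed): 0.547–0.579
- 9/24 against 3/15 (one 80 mg response unconfirmed): 0.861–0.892

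The stated 80.7% is not reproduced by these priors. The model behind it is not given, so this shows sensitivity in either direction and no more.

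**Step 4: can the scheduled scans confirm a response?** With the section 10.4 windows, the shortest gap between the week 6 and week 12 scans is (84 − 7) − (42 + 3) = 32 days. With the ±7 days for week 6 in section 5.3 it is 77 − 49 = 28 days. Both meet a 4-week minimum. A response first seen at week 12 or later waits about 12 weeks for its next scheduled scan.

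**The case against.** The best defence is that 11.4 is incomplete and does not really contradict 11.6. Section 11.6 calls the first observation of a response the first of two confirmatory measurements, so response in this protocol may simply mean confirmed response. On that reading ORR, time to response and duration share the same patients. This is possible, but 11.4 as written does not require it, and neither section supplies an interval.

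Several other limits stand:

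- Time to response and duration appear only as definitions. They are not among the objectives or the section 14 outcomes, and section 3.4 reports no result for them.
- Measurement error does not act in one direction only. A false progression closes the response window early, and an under-measured baseline can hide a true 30% decrease. The upward bias is a tendency.
- The rule behind the historical 25% is unknown. If those responses were unconfirmed, cutting only this trial's numerator would make the comparison less fair.
- Both conclusions in section 3.4 have other support. The historical one also rests on PFS, and the dose preference on PFS and three patient-reported measures.

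A reader might infer that the 35.7% does contain unconfirmed responses. The documents do not say so. A reader might also infer that dose-finding was affected. It was not: in section 14.1, "Efficacy is defined as achieving CR, PR, or stable disease within 6 weeks".

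**Conclusion.** The inconsistency between 11.4 and 11.6 is real and should be resolved. The plan permits unconfirmed responses in ORR; whether any are there cannot be told from the documents, and the number may be zero. The consequence is confined to a secondary outcome in section 14, but one that carries a historical comparison without a control arm and part of a dose comparison.

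The size is conditional. One to three unconfirmed responses among the 15 would take the probability of exceeding 25% from about 0.94 to somewhere between 0.90 and 0.68. This assumes symmetric Beta priors and a fixed historical rate of 25%. It does not show that the stated 96% is wrong.

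**What to change.** For analysis, write one RECIST 1.1 response rule and use it in both 11.4 and 11.6:

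1. A confirmed response is a CR or PR seen again at a later scheduled scan at least 4 weeks after the first.
2. ORR, time to response and duration use the same responders.
3. Responders with no later scan, because they are off treatment or in the extension (where section 11.6 drops formal RECIST measurements), count as unconfirmed.
4. Confirmed and unconfirmed ORR are reported side by side, overall and by dose.
5. The historical comparison is made on whichever line matches the rule behind the 25%, or on both if that rule is unknown.

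This is a cheap improvement: analysis-plan wording and a re-tabulation, with no extra scans. The downside is that confirmed ORR may be lower, and some real responses without a later scan will appear only in the unconfirmed line.

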12.0 CRITERIA FOR REMOVAL FROM PROTOCOL TREATMENT

- Progressive disease: Patients, who develop rapidly progressive disease (clinically or by RECIST) before the scheduled evaluations, may be taken off protocol treatment at the discretion of the investigator. Patients can continue to receive their assigned targeted agent, even if they develop progressive disease radiographically, as long as in the judgment of the treating physician, they are benefitting from their targeted agent.
- Intercurrent illness that prevents continuation of treatment.
- Unacceptable adverse event(s), or delay of treatment for > 4 weeks due to treatment-related toxicity. Note: Patients who require emergency surgery (e.g. for appendectomy or because of trauma complications) or who require a procedure (e.g. Kyphoplasty/vertebroplasty) may remain on trial, even if administration of the targeted agent is interrupted, as long as the targeted agent is resumed within 4 weeks from date of interruption.
- Death
- Patient non-compliance with therapy.
- Decision of the patient to withdraw from the study
- Lost to follow-up
- Imprisonment or the compulsory detention for treatment of either a psychiatric or physical (e.g., infectious disease) illness.

The consequence of study withdrawal is that no new information will be collected from the withdrawn patient and added to the existing data or any database.

13.0 SAFETY ASSESSMENTS AND REPORTING REQUIREMENTS

13.1 All patients will be evaluated for safety. The safety parameters include all laboratory tests and hematological abnormalities, physical examination findings, and spontaneous reports of adverse events reported to the investigator by patients. An adverse event is any untoward or unfavorable medical occurrence in a human subject, including any abnormal sign (for example, abnormal physical exam or laboratory finding), symptom, or disease, temporally associated with the subject's participation in the research, whether or not considered related to the subject's participation in the research. All adverse events encountered after the patient has provided informed consent and until 4 weeks after the patient has stopped treatment will be evaluated according to the NCI Common Toxicity Criteria (CTCAE) version 4.0. Prior treatment associated toxicities present at the time of informed consent but before study treatment initiation, will be recorded as baseline abnormalities and graded according to NCI CTCAE version 4.0 criteria.

Information about all adverse events, whether volunteered by the subject, discovered by investigator questioning, or detected through physical examination, laboratory test or other means, will be collected and reported as described in the data submission schedule

**Reporting Responsibilities of Investigators under 21 CFR 312.64(b) and
Sponsors under 21 CFR 312.32(c)(1)(i) for Serious and Unexpected Suspected**

Proprietary of MD Anderson Cancer Center

Adverse Reactions

Term	Investigator Responsibility	Sponsor Responsibility	Final Determination Responsibility
Serious (or life-threatening)	Yes (Investigator must report all serious adverse events to the sponsor immediately)	Yes	An event is considered serious or life-threatening, based on either the investigator's or sponsor's opinion.
Unexpected	No (No requirement to assess "expectedness")	Yes	The sponsor is responsible for determining whether event meets the definition of "unexpected," based on whether the event is listed in the investigator brochure; or if an investigator brochure is not required or available, is not consistent with the risk information described elsewhere in the general investigational plan or elsewhere in the current application.
Suspected Adverse Reaction – (causality assessment standard - "reasonable possibility")	Yes (Investigator must provide sponsor with an assessment of causality)	Yes (Sponsor's assessment determines reportability, regardless of investigator's assessment)	The sponsor is responsible for determining whether there is a reasonable possibility that the drug caused the adverse event, taking into consideration the investigator's assessment.

The **sponsor** reports serious and unexpected suspected adverse reaction to the FDA and all participating investigators.

